## 4. Methods

**Aim 1: Refine the MiSARA JITAI to reduce cannabis use among EAs.**

This aim does not include human subjects. Instead, it includes the development of (a) therapeutic content and (b) engaging content and human computer interfaces. Using a participatory action approach, we will integrate EA feedback from our formative studies with consultation from a new EA advisory board to create the MiWaves JITAI app.

Refinements may include:

- increased interactivity and personalization of the app,
- integration of data into personalized feedback graphs,
- personalization of messages based on behavioral trends to increase novelty, and
- archiving intervention content in a virtual toolbox and creating 'on-demand' pulls for additional messages.

A collection of empirically- and theoretically-grounded therapeutic content will be identified and developed by multiple intervention experts to maximize engagement. Therapeutic content will harness a variety of mediums and may include: a) messages (targeting goals, strengths; benefits to change, tools to address motives); b) brief videos (e.g., focusing on goal setting and attainment, protective behavioral strategies, safe driving, overdose prevention, other strategies); and c) life-insights visualizations -- feedback capitalizing on Ecological Momentary Assessments (EMAs) to visually integrate information about behaviors, risk and protective factors. Intervention content will be reviewed by an advisory board of EAs and selected based on fit with evidenced-based intervention content (e.g., motivational interviewing) and appropriateness (e.g., no images glamourizing use, offensive jokes). Intervention experts on our team will collaborate with engagement experts, machine-learning experts and HCI experts to further develop and refine various types of visualizations to specifically address cannabis use related risk.

**Aim 2: Conduct a pilot trial to test the feasibility and acceptability of MiWaves, a 2nd generation JITAI with continually optimized population-based decision rules.**

This aim includes human subjects. Specifically, it includes the following: a) conduct EA enrollment and obtain feedback, and b) software refinement. Based on prior work and Aim 1 feedback from EA advisors, the MiWaves app will be iteratively refined among a total of 150 EAs (ages 18-25). Participants who report cannabis use three or more times per week in the past month (see Inclusion/Exclusion criteria below for more information) will be recruited online to use the MiWaves JITAI for 30 days. Enrollment will occur in multiple waves, with the first two waves beta testing proposed trial procedures with small groups of  $n \approx 10$  participants and  $n \approx 20$ , and the final wave(s) involving a pilot trial with up to 150 EAs. Feasibility will be defined by the percentage of participants who consent to the study who ultimately download the MiWaves app.

## **Participants**

The subject population comprises of emerging adults ages 18-25 years-old, residing in the US, who use cannabis, and report motivation to change their cannabis use habits. To ensure representation of both sexes, we will recruit approximately 50% males and 50% females. Using a similar approach to the National Epidemiologic Survey on Alcohol and Related Conditions (NESARC), we will attempt to represent minorities who are African American and Hispanic (~20%). Thus, we expect approximately 67% Caucasian, 20% African American, 3% Asian, 1% Native American/Alaskan Native, 1% Hawaiian/Pacific Islander, and 8% more than one race.

## **Recruitment**

We will employ a variety of recruitment sources on this project. Recruitment options may include:

1. We may use social media ads (e.g., Facebook, Instagram, Snapchat, X [Twitter]) to target 18–25-year-olds in the United States. When users click on our ad, they will be redirected to the online (Qualtrics) screening informed consent (with waiver of documentation of consent and waiver of parental consent requested for states where the age of majority is over 18).
2. We may recruit potential participants through flyers displayed within the community (at locations such as coffee shops, gyms, community centers, clinics, restaurants, libraries, stores or small businesses, pharmacies, churches, etc.).
3. We may recruit potential participants through a page on UMHealthResearch.org, a website hosted by the Michigan Institute for Clinical and Health Research (MICHR). Participants who learn of the study through UMHealthResearch.org may be redirected to the study website and/or the direct link to the screening survey through the study's description. If someone with a UMHealthResearch.org account finds the study and expresses interest in participating, they may be contacted by research staff by phone or email.
4. We may partner with third-party recruitment companies (e.g., BuildClinical) to generate additional leads for our study staff to follow up with.
5. With appropriate regulatory approval from the necessary IRBs, we may contact participants from other studies that consented to recontact for future research participation. In these situations, we will receive approval from that study's investigative team and IRB, and list the IRB number in section 8-1.1 of our application.
6. We may provide sample emails with recruitment resources to distribute to venues (with appropriate approval) such as the UM Registrar email list or other community Listservs.
7. We may recruit potential participants through a study specific website, which may include an embedded eligibility survey.
8. We also may contact interested participants via email or in person with appropriate follow-ups.

Participants will be invited to print or save a copy of the informed consent before moving on to the screening survey. After giving online screening consent and completing a CAPTCHA to protect against bots, participants will complete a 2-3-minute eligibility survey. Following determination of eligibility (see eligibility requirements outlined in inclusion and exclusion criteria section below), negative screens will receive a thank you page ending their participation. No identifying information will be collected from those participants who are not eligible for the study.

#### Inclusion/Exclusion Criteria

Individuals will be eligible to continue if they: 1) reside in the US; 2) speak and read English; 3) are 18-25 years of age; 4) have a smartphone on which the app can be downloaded; 5) screen positive for cannabis use 3 or more times each week over the past month; 6) report motivation to change cannabis use as a 1 or higher (using a scale of 0-10); and 7) meet study verification criteria (i.e., use of CAPTCHA, IP address checks, repeat attempts, social media checks).

Participants may be excluded if they report current medical marijuana use and/or fail identity verification procedures (see prior study) based on IP addresses, survey time completion, repeat attempts, social media checks or survey responses. Potential participants may also be excluded based on participant best interest (e.g., if the participant has plans to travel outside of the country during the app use period, or if study staff know the participant or their family personally, in order to fully ensure participant privacy), with PI approval.

## **Baseline Assessment**

Eligible participants will be notified of their eligibility and asked to provide contact information. Following completion of the screening assessment, participants will be verified for authenticity. We have experience with methods related to identification and handling of fraudulent cases using internet-based research via use of a Completely Automated Public Turing test to tell Computers and Humans Apart (CAPTCHA) and checking for duplicate IP addresses.

Once verified, eligible participants will be redirected to an online baseline consent housed in Qualtrics (waiver of documentation and waiver of parental consent requested for states where the age of majority is over 18). After giving online baseline consent and completing a CAPTCHA to protect against bots, eligible participants will complete a 25-35 minute baseline survey and another contact information form in Qualtrics. In the rare event and at the participant's request, participants may also have the option to complete the consent and surveys over the phone where the research assistant will read the questions and record responses.

After completion of the baseline assessment, eligible participants will receive information about how to download and enroll into the MiWaves app. Eligible participants will have one month from screening consent to complete the baseline assessment and download the MiWaves app. To begin the 30-day pilot trial, participants will be activated to begin receiving notifications. After this step, participants will be enrolled in the study and begin the pilot trial.

## **Pilot Trial**

As part of the pilot trial, participants will interact with the app for a 30-day period. During this intervention period, participants will be asked to complete four short (5-10 minutes) weekly surveys online and brief (1-3 minutes) twice-daily surveys within the app. Participants will receive daily push notification reminders about completing surveys which will not include sensitive information (e.g., about substance use) or other information that may identify the individual as a study participant. The MiWaves app can also passively collect data regarding participants' interaction with the app, movement, context, and may also collect GPS location. Beta testing will occur in the first two waves of n=10 per wave to aid in the development of the app and algorithm creation. Participants involved in beta testing waves will interact with the app for only 10 days including the twice-daily surveys during those 10 days and then complete only one weekly survey.

Since novelty is well understood to enhance user engagement with technology, additional features of the app can be intermittently turned on to maintain participant engagement during the intervention period. These features may include: 1) life insights feedback, or graphs of survey responses/app engagement over a window of time; 2) inspirational messages which harness the theory of reciprocity to encourage survey completion; 3) financial incentives of varied amounts which are tied to survey completion; and 4) active tasks, which are brief games that capture cognitive performance (e.g., reaction time, spatial memory). In instances where the app is not able to display how many surveys have been completed and how much money participants have earned during the pilot trial (e.g., due to technical difficulties), participants will receive a message each week from the study team that informs them: 1) how many

assessments they completed during the past week; and 2) the total amount of money earned to date.

Participants will likewise receive therapeutic content via the app during the pilot trial. Twice per day (morning and afternoon), intervention messages may be delivered. MiWaves will use reinforcement learning algorithms to learn whether and in which context it is best to deliver these messages for each EA. The message will target content areas such as daily goals to reduce use, upstream factors (e.g., coping with negative affect), reasons and tools to reduce use, potential consequences of use, and identification of alternative activities. Messages will vary by the amount of effort required by the EA to engage with the content (e.g., messages with a 'pick' list or text entry box will be considered higher effort, whereas messages with only visual content will be considered lower effort), as a potential moderator of intervention effects. Furthermore, harm reduction messages can be delivered when the EA enters a high-risk location (e.g., dealer's/dispensary location). These high-risk locations will be prespecified during app set-up. Note that all content participants receive directly on their phone as push notifications will not contain any confidential information. All intervention messages will include user ratings (e.g., thumbs up/down, star rating) to inform future content refinement.

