## 2. Objectives

Given that cannabis use peaks among EAs and changing norms and policies have led to increases in availability and reductions in perceived risks of cannabis use, we aim to develop a JITAI to reduce cannabis use among non-treatment seeking EAs who use cannabis thrice weekly. Using a transdisciplinary approach, the JITAI will integrate empirically based intervention strategies for reducing substance use (e.g., motivational interviewing and mindfulness) with engagement strategies grounded in areas such as basic psychology, human computer interaction (HCI), and marketing, which are necessary for efficacious mHealth interventions.

In this study, we will innovatively build on the results from our prior MRT optimizing app engagement (SARA) and prior feasibility/acceptability pilot of a prototype JITAI (MiSARA JITAI). In Aim 1, based on participant feedback, we will refine the MiSARA JITAI app environment to improve engagement by increased interactivity and personalization to maintain novelty throughout the intervention period. Then, we will test the feasibility, acceptability, and preliminary efficacy of a person specific JITAI called MiWaves for reducing cannabis use in this critically important EA population.

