**Table 1. Overview of MiWaves Measures, Assessment Timepoints, and Question Timeframes**

Domain	Assessment Timepoint					
	Screen	Baseline	Weekly	Daily	Post-Test	2M FU
Background Characteristics						
Demographics 	Current	Current				Current
Cell phone characteristics 	Current					
Substance Use Frequency, Quantity and Methods of Use						
Nicotine use 	1M	1M			1M	1M
Nicotine methods of use 		1M			1M	1M
Alcohol use QxF 	1M	1M		Yesterday	1M	1M
Alcohol TLFB 		7D	7D			7D
Cannabis use QxF 	1M	1M	7D	12h	1M	1M
Cannabis TLFB 		7D	7D			7D
Cannabis methods of use 			1M		1M	1M
Illicit drug use 			1M		1M	1M
Prescription drug misuse 			1M		1M	1M
Precursors of Cannabis Use						
Cannabis use motives 		Current		12h		Current
Cannabis cravings 		Current		Current		Current
Perceived risk of cannabis 		Current				Current
Social influences 		Current				Current
Mood/Affect 			7D	Current		
Stress 				Current		
Energy 				Current		
Readiness to Change Substance Use						
Importance rulers (nicotine, alcohol, cannabis) 	Current	Current			Current	Current
Likelihood and confidence rulers (cannabis) 		Current				Current
Substance Use Outcomes and Consequences						
Marijuana Adolescent Consequences Questionnaire 		1M			1M	1M
Young Adult Driving Questionnaire 		1M			1M	1M
DSM Symptoms Checklist 		1M			1M	1M
Protective Factors						
Protective Behavioral Strategies for Marijuana 		1M	7D		1M	1M
Social Support 		Current				Current
Behavioral Economic Measures						
Cannabis Purchase Task 		Current	Current			Current
Activity Level Questionnaire 		1M			1M	1M
Delayed Discounting Task 		Current	Current			Current
Brief Relative Reinforcement*			7D			
Mediators						
Social context of cannabis use 		7D	7D			7D

Domain	Assessment Timepoint					
	Screen	Baseline	Weekly	Daily	Post-Test	2M FU
Satisfaction with social events 				Current		
Distress 				Current		
Positive outlook 				Current		
Health Status, Outcomes and Service Utilization						

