Service Utilization 		Lifetime				2M
Mental Health						
Global Measure 		Current				Current
PHQ-2 		2W	7D		2W	2W
GAD-2 		2W	7D		2W	2W
ASI-3 		Current				
Mindfulness Attention Awareness Scale 		Current				Current
PCL-5 short form 		1M				1M
Physical Health						
Global Measure 		Current				Current
Pain Intensity 		7D				7D
Pain Interference 		7D				7D
Sleep Quality 		7D				7D
Sleep*				12h		
Exercise 				12h		
Acceptability and Feasibility (Primary Outcome Measures)						
Acceptability 105,*					Current	
Feasibility						

\*Items were created for this study

Notes: In the table above, 1M = Past Month, 2W = Past 2 weeks, 7D = Past 7 days, 12h = Past 12 hours.

Bolded items indicate Primary Outcome Measures. All other outcomes are exploratory.

Table cells which are blank indicate that the domain was not assessed at that timepoint.

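### Does the fixed 12-hour look-back of the daily cannabis item stop the trial from separating the effects of the morning and afternoon messages?

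*Combined protocol and SAP*

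**What the plan says.** The Pilot Trial section of the combined protocol and SAP sets up to two message occasions a day: "Twice per day (morning and afternoon), intervention messages may be delivered". A reinforcement learning algorithm is to "learn whether and in which context it is best to deliver these messages for each EA". Messages differ in the effort they ask for, and effort is named "as a potential moderator of intervention effects". Participants also complete "brief (1-3 minutes) twice-daily surveys within the app".

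In the Daily column of Table 1, the rows "Cannabis use QxF" and "Cannabis use motives" are both coded 12h, and the table notes define "12h = Past 12 hours". The other cannabis use measures (the timeline follow-back, and the quantity-frequency item outside the Daily column) look back 7 days or one month. The daily 12h item is therefore the only measure of the amount used within a day. Craving is also asked daily, but as a current state.

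Section 2 (Objectives) mentions testing the "preliminary efficacy of a person specific JITAI called MiWaves for reducing cannabis use". The Measures section makes every Table 1 outcome exploratory apart from feasibility and acceptability, and Section 5 (Analysis) promises only descriptive statistics and exploratory modelling. The documents give no clock times for messages or surveys, no rule tying a report to a message, no proximal outcome and no reward for the algorithm.

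**The concern.** A morning and an afternoon message will usually be less than 12 hours apart. On an assumed grid of whole hours, with morning from 06:00 to 11:00 and afternoon from 12:00 to 18:00, 41 of the 42 pairs are closer than 12 hours and one is exactly 12. A 12-hour window cannot fit inside a shorter interval. Every report that covers the hours between the two messages must therefore take in some hours from before the first or after the second.

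If the trial wants to know whether a single message reduced use, or whether high-effort messages work better than low-effort ones, this looks damaging. Two messages of different effort could fall in one report. A morning effect could be watered down by hours that belong to another occasion. If the algorithm learned from this item, its learning would suffer too. A look-back cannot be changed once the data are collected.

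**Working it through.** **Inputs.** From the documents: two message occasions a day, two surveys a day, a 12-hour look-back. Assumed, because not stated: the gap g between the morning and afternoon occasions (4, 6, 8 or 10 hours); even use of 0.125 per hour; a true 20% reduction; each message sent with probability 0.5, independently. The plan states no figure of its own to reproduce.

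**Step 1: can a report fit between the messages?** Put the morning occasion at hour 0, the afternoon at hour g and the next morning at hour 24. A report at hour S covers S − 12 to S. It lies wholly between the two messages only if 12 ≤ S ≤ g, which needs g of at least 12. For shorter gaps, at least 12 − g hours fall outside.

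| g (h) | least hours outside | largest share between the messages, g/12 |
|---|---|---|
| 4 | 8 | 33% |
| 6 | 6 | 50% |
| 8 | 4 | 67% |
| 10 | 2 | 83% |

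This part of the concern is correct.

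**Step 2: does survey timing matter?** Yes. A report excludes use before the morning message whenever S ≥ 12, for any g. At S = 12 it holds g hours from the morning interval and 12 − g hours after the afternoon occasion, all of them after the morning message. If no afternoon message is sent that day, there is no second message to mix with.

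If the surveys are instead taken at the message times, consecutive reports overlap by 12 − g hours in the daytime. The first 12 − g hours after the afternoon survey are then never asked about: 8/20 = 40%, 6/18 = 33%, 4/16 = 25% and 2/14 = 14% of that interval. Which case applies is not stated.

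**Step 3: where the dilution comes from.** Suppose the morning effect stops at the afternoon decision point, sent or not. Average use in the other 12 − g hours is then 1 − 0.5 × 0.2 = 0.9 of the base rate. A plain comparison of reports with and without a morning message shows 0.2g / (0.9(12 − g) + g):

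- g = 4: 0.8/11.2 = 7.1%
- g = 6: 1.2/11.4 = 10.5%
- g = 8: 1.6/11.6 = 13.8%
- g = 10: 2.0/11.8 = 16.9%

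**Step 4: relax each assumption, with the report at hour 12.**

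- *The effect lasts 12 hours.* Use with a morning message is 0.8 × (g + 0.9(12 − g)) and without one g + 0.9(12 − g), taking the two effects to multiply. The ratio is 0.8, so the full 20% shows at every g.
- *The effect stops at the afternoon occasion, but both messages are modelled.* With hourly rate r, the expected count is 12r − 0.2gr × (morning sent) − 0.2(12 − g)r × (afternoon sent). The morning reduction is 12 × |morning coefficient| / (g × intercept). At g = 8 and r = 0.125 the intercept is 1.5 and the coefficient is −0.2, so 12 × 0.2 / (8 × 1.5) = 20%.

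Simulation on these settings (120 people, 30 days, 400 runs) agrees with both results to within sampling error.

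**Step 5: what is left.** The loss is in precision. In simulation, the 12h item carried 31%, 46%, 61% and 77% of the information on a short-lived morning effect that an item asking about use since the last decision point would carry, at g = 4, 6, 8 and 10.

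**Step 6: the cost of that other item.** Its overnight look-back would be 24 − g = 20, 18, 16 and 14 hours, sleep included. The two daily intervals would be unequal, and surveys would have to be tied to the decision points.

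**The case for a change.** The strongest case for acting is that the geometry in Step 1 is beyond dispute and the plan shows interest in message-level questions by naming effort as a moderator. Setting aside days with an afternoon message is not a clean escape, because the algorithm may choose afternoon delivery in response to what followed the morning message. The same caution applies to the two-message model. It recovers the effect when afternoon delivery is independent of that intervening context, or when the context is properly adjusted for, and it needs the gap to be known. An item anchored to the last decision point would add no questions and would carry more information about a short-lived morning effect.

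Much of this stands. A single 12h report cannot isolate the hours between two messages less than 12 hours apart, and precision for that narrow contrast is reduced. What does not stand is the stronger claim that no survey time can isolate use after the morning message, since any report at least 12 hours after it does so. Nor is dilution inherent in the item: it needs both an effect that stops at the afternoon occasion and an analysis that ignores the second message. Message content includes goals for the day, so an effect lasting beyond the afternoon is plausible, though the documents do not settle it.

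The efficacy aim in Section 2 concerns the intervention as a whole. Effort is only a potential moderator and has no outcome attached. Whether the algorithm uses the 12h item is unknown, so harm to its learning cannot be asserted.

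**Conclusion.** No change to the plan follows. The schedule and look-back are as described, and for gaps of 4 to 10 hours between 8 and 2 hours of any report must lie outside the morning-to-afternoon interval. The fall from 20% to between 7.1% and 16.9% is conditional on the assumed rates, an effect that ends at the afternoon occasion and an unscaled comparison. Drop either of the last two and, with a report 12 hours after the morning message, it disappears. The remaining cost is precision in an exploratory within-day contrast that the plan does not commit to.

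What is missing is detail: when messages and surveys occur and how they are linked. An analyst studying single messages would need those times, and would choose between a joint model and a day-level analysis accordingly. A uniform 12-hour recall against unequal intervals with 14 to 20 hours of overnight recall is a fair trade-off on which statisticians can differ. Feasibility, acceptability and the weekly timeline follow-back totals are unaffected. Daily totals built by adding two 12h reports would be sound only if the surveys are 12 hours apart.
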